4.4. Subject Withdrawals

In all circumstances, subjects will be made aware of their right to refuse participation in a clinical study and are entitled to freely withdraw their informed consent, without giving reasons. Subjects should be assured that withdrawal from the study will not cause prejudice, will not result in any determinant, and will not affect treatment. In addition, refusal to give consent or withdrawal of consent to participate in research must not lead to any liability or discrimination (e.g., with regard to insurance or employment) against the person concerned.

It is important to note that it is impossible for the GT005 product to be removed from the subretinal space after injection. Therefore, once surgery has taken place, subjects can withdraw from the study but cannot withdraw from treatment.

The Investigator also has the right to withdraw subjects from the study (e.g., in the case of non-compliance with the protocol and/or lack of willingness or commitment to co-operate in all phases of the study, or in the case of an AE which is considered intolerable by the subject and/or legal representative). Long-term safety assessment of subjects treated with a gene therapy product is a regulatory requirement and every effort will be made to at least continue monitoring long-term subject safety.

Should a subject decide to withdraw for any reasons, all efforts will be made to complete and report the observations as thoroughly as possible. A complete final evaluation at the time of withdrawal will be performed with an explanation of the exact reason why the subject is withdrawing from the study.

The Investigator is responsible for the optimal individual treatment of the subject.

The Investigator must fill in the “early termination visit” in the electronic case report form (eCRF) explaining all reasons for withdrawal.

If the subject withdraws consent, the Sponsor may retain and continue to use any data collected before withdrawal of consent.

The Investigator will provide or arrange for appropriate follow-up (if required) for subjects withdrawing from the study. After a subject withdraws from the study, the Investigator is still responsible for reporting SAEs considered causally related to the study drug. In addition, the Investigator needs to ensure appropriate treatment and follow-up of each AE still ongoing at the time of the subject's discontinuation.

All subjects participating in the clinical study will receive an alert card from the Investigator, which has been previously agreed by the Sponsor and approved by the Ethics Committee. At a minimum it will contain the name of the subject, the Investigator contact number and information regarding the medical treatment received by the subject.

Whether a subject is withdrawn from the study at their own request or based on a decision of the Investigator, follow-up should be maintained, subject to the consent of the subject.

4.4.1. Replacements

[figure not shown]
Subjects who are eligible but do not receive treatment will be classed as screen failures and may be replaced. A subject can be screened twice if the reason for ineligibility is transient (e.g., a cataract requiring cataract extraction), to allow the 8-week time interval between baseline assessment of the screening visit and dosing to be maintained. Furthermore, subjects with borderline screening assessments (e.g., laboratory parameters) can be re-tested once within the assigned screening period.

In the event, that a subject withdraws from the study for any reason other than an AE or other safety concern or is lost to follow-up within 6 months (Week 24) post-dosing, the subject may be replaced. The reason for the subject's withdrawal from the study must be recorded.

5. CONCOMITANT MEDICATIONS

5.1. Permitted Concomitant Medications

During the course of the study, subjects will be allowed to continue taking all prescribed and non-prescribed medications, unless excluded as per the study protocol. Note that AREDS based supplements are permitted as no effect on progression of GA has been reported.

Prior to administering the corticosteroid therapy, Investigators must refer to relevant Summary of Product Characteristics (SmPC) and/or label guidance for use.

Concomitant medications will be checked throughout the study and any change in medication after the date on which the subject signs the informed consent should be recorded in the eCRF.

5.2. Non-permitted Concomitant Medications

There are no contraindicated medications for GT005 treatment. Potential subjects who previously received a gene/cell-based therapy at any time are excluded.

6. TREATMENT(S)

6.1. Appearance and Content

GT005 is supplied as a single vial containing [REDACTED] of AAV2 virus vector expressing hCFI.

6.2. Dosage and administration

6.2.1. Dosage

GT005 will be administered at one of three dose levels:

- Low dose: [REDACTED]
- [REDACTED]
- [REDACTED]

6.2.2. Administration

The product is delivered by trained vitreoretinal surgeons as a single administration by subretinal injection under local anaesthesia. Other anaesthetic options will be considered by the surgeon as appropriate for the subject. The injection volume will be 0.1mL.

For more information, contact the Office of the Vice President for Research and Economic Development at [contact] or [contact].

© 2019 Pearson Education, Inc.

1. **What is the primary purpose of the study?** (Please select one)

Digitized by [contact]

© 2010 Pearson Education, Inc. All Rights Reserved. May not be reproduced, in whole or in part, without permission of the publisher.

For more information, contact the Office of the Vice President for Research and Economic Development at [contact] or [contact].

© 2013 Pearson Education, Inc.

For more information, contact the Office of the Vice President for Research and Economic Development at [contact] or [contact].

For more information, contact the Office of the Vice President for Research and Economic Development at [contact] or [contact].

Digitized by [contact]

For more information, contact the Office of the Vice President for Research and Economic Development at [contact] or [contact].

For more information, contact the Office of the Vice President for Research and the Office of the Vice President for Student Affairs.

© 2013 Pearson Education, Inc.

© 2019 Pearson Education, Inc.

6.3. Packaging

6.3.1. GT005

GT005 and diluent are both supplied in single vials in an appropriately labelled carton as the secondary container. GT005 and diluent will be stored at $\leq -60^{\circ}\text{C}$.

6.3.2. Orbit Subretinal Delivery System (US only)

[REDACTED]

Further details regarding the Orbit SDS are provided in the Instructions for Use and the Orbit SDS Surgical Procedure Manual.

6.4. Labelling

6.4.1. GT005

All study medications will be labelled in accordance with Annex 13: Manufacture of investigational products and specific local requirements.

6.4.2. Orbit Subretinal Delivery System (US only)

All study devices are labelled in accordance with FDA regulations for marketed products. The label contains key elements such as part number, lot number, and expiration date. A label stating, 'For use in clinical trial GT005-01' and site specific information is applied to the shipping container.

6.5. Investigational Medicinal Product Supply Chain

GT005 and diluent will be dispatched directly to sites from either UK or the US approved 3rd party distribution depots.

6.6. Blinding and Randomisation

This is an open label study. All participants will receive GT005.

6.7. Treatment Compliance

GT005 is delivered as a single administration by subretinal injection. The subretinal injection is undertaken by a qualified vitreoretinal surgeon at a surgical site. The Investigator at the surgical site is responsible for ensuring GT005 is handled in accordance with the protocol and is only administered to subjects enrolled into the study. Additionally, the Investigator at the surgical site is responsible for ensuring the Orbit SDS is handled in accordance with the relevant Surgical Manual and is only administered to subjects enrolled into the study.

6.8. Drug Storage

GT005 is supplied in a single vial in an appropriately labelled carton as the secondary container and stored at ≤ -60°C.

Prior to administration, GT005 will be thawed at ambient temperature (15 to 25°C). Once thawed, GT005 should be held at ambient temperature and must be administered within the same business day of thaw and preparation. GT005 should be handled as per the Pharmacy Manual.

6.9. Drug and Surgical Device Accountability

GT005 and all applicable surgical devices will only be delivered to the investigational site.

All material supplied is for use only in this clinical study and should not be used for any other purpose.

The Investigator or designee is responsible for GT005 accountability, reconciliation and record maintenance. The Investigator or designated site staff must maintain accountability records throughout the course of the study including records of the amount of GT005 received, the identification of the subject for whom it was dispensed and the date(s) and quantity of GT005 dispensed, and doses and volumes administered.

These records must be available for inspection by a study monitor during the study.

GT005 is a biosafety level 1 product. GT005 post-administration measures regarding destruction and disposal of GT005 and disposables are detailed in the Pharmacy Manual.

The Investigator or designated staff member is responsible for maintaining inventory of the Orbit SDSs used. A record will be kept of the identification of Orbit SDSs, and the identification of the subject for whom the device was used.

At the end of study enrolment, unused and unopened devices should be returned to the Sponsor and recorded in the accountability records. Accountability records must show the identification and quantity of devices returned and method of shipment (US only).

7. STUDY PLAN

The timing and type of assessments required during the study are summarised in the Schedule of Assessments [[Table 1: Clinical Schedule \(Screening to Week 48\)](#); [Table 2: Schedule of Visual Tests \(Screening to Week 48\)](#); [Table 3: Follow-up Schedule \(Week 72 to Week 240\)](#)].

Definition of Local Site versus Surgical Site

Local investigational sites are defined as sites that are approved to participate in this clinical study but require identified subjects to be transferred for surgery. Subject consent, screening, and post-operative follow-up visits will be conducted according to the visit schedule outlined in the schedule of assessments.

Surgical sites are defined as sites that are approved to participate in this clinical study and to perform the surgical procedure as part of this clinical protocol.

Dependent upon location and Sponsor approvals, a surgical site may also act as a local site. In such cases, all study visits and assessments (as listed in [Table 1](#), [Table 2](#), [Table 3](#)) for all timepoints, inclusive of Long-Term Follow-Up, will take place at the surgical site.

7.1. Visit 1 Screening (Day -56 to -1 [-8 weeks]); at Local Site (may be conducted over several days):

The Investigator will explain the study purpose, procedures, and subject responsibilities to each potential study subject. The subject's willingness and ability to meet the protocol requirements will be determined. Prior to any study-specific procedure, written informed consent will be obtained.

The subject will sign and date one copy of the consent form in the presence of the Investigator or his/her designee. The original signed form will be retained at the study site and an additional copy will remain in the subject's medical records; a copy will also be given to the subject.

Data from subjects screened in another Gyroscope sponsored study, conducted at the same Investigative site as the FOCUS study, may be used to fulfil the screening and eligibility requirements for this study. This is only permissible if the screening data are collected within the screening period specified in the clinical protocol. Should subjects fail to meet the eligibility for FOCUS, they will be classed as screen failures for this study and may be considered for entry into another Gyroscope sponsored study (see [Section 4.4.1](#)).

After informed consent has been obtained, the subject will be evaluated to determine eligibility. Screening procedures will consist of the following:

Inclusion/Exclusion (screen failures to be recorded), recording of demographics, medical/surgical history and concomitant medication. A urine pregnancy test (only for

women of childbearing potential), vital signs, and AEs will be completed prior to the following procedures:

- Blood draws for:
 - Biochemistry and haematology
 - Serum CFI Levels (central laboratory, baseline measurement only)
 - [REDACTED]
 - [REDACTED]
 - Sequencing of complement genes. **Note: this assessment is applicable to all subjects at the Screening Visit unless already completed in another Gyroscope sponsored study.**
 - [REDACTED]
 - [REDACTED]
- Standard Ophthalmic Examination including indirect ophthalmoscopy, a slit-lamp examination, IOP measurement, assessment of anterior chamber and vitreous inflammation, and cataract grading
- Colour fundus photography (CFP)
- FAF
- OCT macula
- OCT-A; if the site does not have OCT-A other imaging modalities may be used to rule out CNV. In the event, that the OCT/OCT-A images are inconclusive to rule out the presence of CNV the subject will be required to undergo an additional assessment via FA
- FA; if OCT/OCT-A images are inconclusive to rule out CNV. FA may also be performed initially prior to OCT/OCT-A results being available, but this is not mandatory
- Microperimetry (assessment can be carried out over two days)
Note: microperimetry is only applicable at sites with a macular integrity assessment (MAIA) microperimeter

- Visual acuity (BCVA and LLVA) using ETDRS
- [REDACTED]
- [REDACTED]

Eligibility assessment and confirmation

Subject eligibility will be confirmed by the Sponsor on the basis of the following criteria:

- GA lesions characteristics assessed by the central reader on the study eye
- BCVA of the study eye
- Investigator statement that the other eligibility criteria are met

The vitreoretinal surgeon will also confirm the study eye.

Subjects whose eligibility is confirmed will be enrolled into the study, assigned a subject number and scheduled for surgery within 8 weeks of screening. The 8-week screening period may be extended up to a maximum of 12 weeks, if agreed by the Sponsor Medical Monitor.

If the screening period is extended past the original 8-week screening period (8–12 weeks), standard ophthalmic exam, haematology/biochemistry, and visual acuity (BCVA/LLVA) assessments should be repeated. In the event, that GT005 administration is deferred during the surgical procedure (e.g., due to an AE occurring during surgery) the screening period may be extended up to 16 weeks if agreed by the Sponsor Medical Monitor. Additionally, if the screening period is extended past 12 weeks (12–16 weeks), in case of GT005 deferral, standard ophthalmic exam, haematology/biochemistry, visual acuity (BCVA/LLVA), and FAFs will be repeated.

Visit 2 will occur at a surgical site. Pre-surgery assessments will include any local requirements of the surgical site. Pre-surgery assessments should be performed within 7 days prior to surgery. The following assessment are also required pre-surgery:

Timing	Procedure
Prior to Entering the Operating Room (within 7 days prior to surgery)	
• Review of Medical/Surgical History including bleeding history• Vital signs• AE/SAE monitoring• Pre-surgery ocular safety check to verify there are no new ocular AEs that would halt surgery• Microperimetry, if this was omitted at screening, should be performed if feasible• Concomitant medication review including use of anti-thrombotic drugs■ [REDACTED]■ [REDACTED]• Urine pregnancy test (for women of childbearing potential) if the one performed at screening is more than 14 days old• Blood draw for:■ [REDACTED]• Visual acuity check:
○ A visual acuity check using ETDRS or Snellen chart (near card is permissible) must be performed on the study eye if >4 weeks have lapsed since the last BCVA with ETDRS assessment. If Snellen result is >3 lines (BCVA equivalent to 15 letters) worse than the previous BCVA ETDRS score, then a BCVA with ETDRS assessment must be repeated. If the BCVA ETDRS score in the study eye is either >15 letters worse than the previous BCVA ETDRS score or <24 letters score (Cohorts 4 to 7), the surgery must be postponed

7.2. Visit 2 Day 2 (Post-Operative discharge); at a Surgical Site:

Subjects will be maintained in the clinic for up to 24 hours following the subretinal injection to assess any acute issues resulting from the surgery. The following post dosing assessments will be performed:

About 24 hours after dosing and prior to discharge	
• AE/SAE monitoring• Concomitant medication review• Standard ophthalmic examination• OCT macula■ [REDACTED]• [REDACTED]■ [REDACTED]■ [REDACTED]■ [REDACTED]• Vital signs
--	---

The subject will be reminded to use two forms of contraception (one of which being a barrier method) for 90 days for men and women of childbearing potential (see Section 8.3).

7.3. Telephone Call; from a Surgical Site:

Each participant must be contacted by telephone to assess [REDACTED] and AEs/SAEs within the following week post dosing.

7.4. Visit 3 (Week 1 ± 3 days); at a Surgical Site:

Recording of: concomitant medication, vital signs, AEs.

The following procedures will be carried out:

- Blood draw for:
 - Biochemistry and haematology
- [REDACTED]
- Standard ophthalmic examination
- OCT macula
- [REDACTED]
- OCT-A if clinically indicated (if a subject converts to wet AMD)
- FA if clinically indicated (if a subject converts to wet AMD). FA is only required if OCT/OCT-A images are inconclusive to rule out the presence of CNV. However, FA may also be performed prior to the OCT/OCT-A results being available, but this is not mandatory
- BCVA using ETDRS
- [REDACTED]

7.5. Telephone Call (Week 2 ± 3 days); from a Surgical Site:

Each participant must be contacted by telephone to [REDACTED]
[REDACTED] AEs/SAEs 14 days (Week 2) post dosing.

7.6. Visit 4 (Week 5 -7/+3 days); at Local or Surgical Site:

At Week 5, subjects may choose to attend a local site or surgical site for clinical assessments and ophthalmic imaging, with review of images by both the local site Investigator and the surgeon.

Recording of: concomitant medication, vital signs, AEs.

The following procedures will be carried out:

- Blood draw for:
 - Biochemistry and haematology
 - [REDACTED]
 - [REDACTED]
 - [REDACTED]
- Standard ophthalmic examination
- FAF
- OCT macula
- [REDACTED]

- OCT-A if clinically indicated (if a subject converts to wet AMD)
- FA if clinically indicated (if a subject converts to wet AMD). FA is only required if OCT/OCT-A images are inconclusive to rule out the presence of CNV. However, FA may also be performed prior to the OCT/OCT-A results being available, but this is not mandatory
- BCVA using ETDRS

■ [REDACTED]

■ [REDACTED]

■ [REDACTED]

7.7. Visit 4.1 (Week 8 ± 7 days); at Local Site or Surgical site:

Recording of: concomitant medication, AEs.

The following procedures will be carried out:

- Standard ophthalmic examination
- Visual acuity (BCVA) using ETDRS
- OCT-A if clinically indicated (if a subject converts to wet AMD)
- FA if clinically indicated (if a subject converts to wet AMD). FA is only required if OCT/OCT-A images are inconclusive to rule out the presence of CNV. However, FA may also be performed prior to the OCT/OCT-A results being available, but this is not mandatory

■ [REDACTED]

■ [REDACTED]

7.8. Visit 5 (Week 12 ± 7 days); at Local Site or Surgical site:

Recording of: concomitant medication, vital signs, AEs.

The following procedures will be carried out:

- Blood draw for:
 - Biochemistry and haematology
 - [REDACTED]
 - [REDACTED]
- Standard ophthalmic examination
- CFP
- FAF

- OCT macula
- [REDACTED]
- OCT-A if clinically indicated (if a subject converts to wet AMD)
- FA if clinically indicated (if a subject converts to wet AMD). FA is only required if OCT/OCT-A images are inconclusive to rule out the presence of CNV. However, FA may also be performed prior to the OCT/OCT-A results being available, but this is not mandatory
- Visual Acuity (BCVA and LLVA) using ETDRS
- Microperimetry **Note: microperimetry is only applicable at sites with a MAIA microperimeter**

■ [REDACTED]

■ [REDACTED]

■ [REDACTED]

■ [REDACTED]

7.9. Visit 6 (Week 24 ± 7 days); at Local Site:

Recording of: concomitant medication, vital signs, AEs.

The following procedures will be carried out:

- Blood draw for:
 - Biochemistry and haematology
 - [REDACTED]
 - [REDACTED]
- Standard ophthalmic examination
- CFP
- FAF
- OCT macula
- [REDACTED]
- OCT-A if clinically indicated (if a subject converts to wet AMD)
- FA if clinically indicated (if a subject converts to wet AMD). FA is only required if OCT/OCT-A images are inconclusive to rule out the presence of CNV. However, FA may also be performed prior to the OCT/OCT-A results being available, but this is not mandatory

- Microperimetry. **Note: microperimetry is only applicable at sites with a MAIA microperimeter**
- Visual acuity (BCVA and LLVA) using ETDRS

[figure not shown]

7.10. Visit 7 (Week 36 ± 7 days); at Local Site:

Recording of: concomitant medication, vital signs, AEs.

The following procedures will be carried out:

- Blood draw for:
 - Biochemistry and haematology
- CFP
- FAF
- OCT macula
- OCT-A if clinically indicated (if a subject converts to wet AMD)
- FA if clinically indicated (if a subject converts to wet AMD). FA is only required if OCT/OCT-A images are inconclusive to rule out the presence of CNV. However, FA may also be performed prior to the OCT/OCT-A results being available, but this is not mandatory
- Visual Acuity (BCVA and LLVA) using ETDRS

7.11. Visit 8 (Week 48 ± 7 days); at Local Site:

At this visit subjects will be invited to consent for additional follow-up for up to -5 years post-dosing. If a subject does not agree to consent to long-term follow-up as part of this study, any ongoing AEs will be followed until resolution with subject consent.

Recording of: concomitant medication, vital signs, AEs.

The following procedures will be carried out:

- Blood draw for:
 - Biochemistry and haematology
 - [REDACTED]
 - [REDACTED]
- Standard ophthalmic examination
- CFP
- FAF
- OCT macula
- [REDACTED]
- OCT-A if clinically indicated (if a subject converts to wet AMD)
- FA if clinically indicated (if a subject converts to wet AMD). FA is only required if OCT/OCT-A images are inconclusive to rule out the presence of CNV. However, FA may also be performed prior to the OCT/OCT-A results being available, but this is not mandatory
- Microperimetry. **Note: microperimetry is only applicable at sites with a MAIA microperimeter**
- Visual acuity (BCVA and LLVA) using ETDRS
- [REDACTED]
- [REDACTED]
- [REDACTED]

7.12. Visit 9 (Week 72 ± 30 days); at Local Site:

Recording of: concomitant medication and AEs.

The following procedures will be carried out:

- Standard ophthalmic examination
- CFP
- FAF
- OCT macula

- OCT-A if clinically indicated (if a subject converts to wet AMD)
- FA if clinically indicated (if a subject converts to wet AMD). FA is only required if OCT/OCT-A images are inconclusive to rule out the presence of CNV. However, FA may also be performed prior to the OCT/OCT-A results being available, but this is not mandatory
- Microperimetry. **Note: microperimetry is only applicable at sites with a MAIA microperimeter**
- Visual acuity (BCVA and LLVA) using ETDRS
- [REDACTED]
- [REDACTED]

7.13. Visit 10 (Week 96 ± 30 days); at Local Site:

Recording of: concomitant medication and AEs.

The following procedures will be carried out:

- Standard ophthalmic examination
- CFP
- FAF
- OCT macula
- OCT-A if clinically indicated (if a subject converts to wet AMD)
- FA if clinically indicated (if a subject converts to wet AMD). FA is only required if OCT/OCT-A images are inconclusive to rule out the presence of CNV. However, FA may also be performed prior to the OCT/OCT-A results being available, but this is not mandatory
- Microperimetry. **Note: microperimetry is only applicable at sites with a MAIA microperimeter**
- Visual acuity (BCVA and LLVA) using ETDRS
- [REDACTED]
- [REDACTED]
- [REDACTED]
- [REDACTED]

- [REDACTED]

7.14. Visit 11 (Week 144 ± 30 days); at Local Site:

Recording of: concomitant medication and AEs.

The following procedures will be carried out:

- Standard ophthalmic examination
- CFP
- FAF
- OCT macula
- OCT-A if clinically indicated (if a subject converts to wet AMD)
- FA if clinically indicated (if a subject converts to wet AMD). FA is only required if OCT/OCT-A images are inconclusive to rule out the presence of CNV. However, FA may also be performed prior to the OCT/OCT-A results being available, but this is not mandatory
- Microperimetry. **Note: microperimetry is only applicable at sites with a MAIA microperimeter**
- Visual Acuity (BCVA and LLVA) using ETDRS

- [REDACTED]

- [REDACTED]

- [REDACTED]

- [REDACTED]

- [REDACTED]

7.15. Visit 12 (Week 192 ± 30 days); at Local Site:

Recording of: concomitant medication and AEs.

The following procedures will be carried out:

- Standard ophthalmic examination
- CFP
- FAF
- OCT macula

7.16. Visit 13 (Week 240 ± 30 days); at Local Site:

Recording of: concomitant medication and AEs.

The following procedures will be carried out:

- Standard ophthalmic examination
- CFP
- FAF
- OCT macula
- OCT-A if clinically indicated (if a subject converts to wet AMD)
- FA if clinically indicated (if a subject converts to wet AMD). FA is only required if OCT/OCT-A images are inconclusive to rule out the presence of CNV. However, FA may also be performed prior to the OCT/OCT-A results being available, but this is not mandatory
- Microperimetry. **Note: microperimetry is only applicable at sites with a MAIA microperimeter**
- Visual acuity (BCVA and LLVA) using ETDRS
- [REDACTED]
- [REDACTED]

- [REDACTED]
- [REDACTED]
- [REDACTED]

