11.3.2. Efficacy

Efficacy assessments to evaluate the anatomical and functional visual outcomes involve: GA area size (via FAF), [REDACTED]
[REDACTED], macular mean sensitivity via Microperimetry, [REDACTED]

For continuous efficacy variables the change from baseline will be derived and presented together with actual values over time (visit) by dose and route of administration and by eye (Treated [Study Eye]/Untreated [Fellow Eye]). Categorical variables from any ocular evaluations will be presented by classification over time (visit) by dose and route of administration and by eye (Treated [Study Eye]/Untreated [Fellow Eye]).

The GA area size data will be compared to historical data on natural disease progression, including pre-treatment data from FOCUS subjects if available.

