##### 3.1.1. Study days and visit windows

Study day is defined as the number of days relative to the date of the subretinal injection with the study drug. For a particular date, study day will be calculated as follows:

- for dates on or after the date of study treatment: Study day = Assessment date – Date of treatment administration + 1;
- for dates prior to the date of administration of study treatment: Study day = Assessment date – Date of treatment administration.

Baseline values are defined as values from the last assessment prior to surgery for the study treatment administration. All data collected after the treatment administration are defined as post-baseline.

The end of study date is the date when a patient completes or discontinues the study. For reporting data by visit in outputs, the end of study visit will be allocated to the actual (reported) visit number. If the end of study date is not on a scheduled visit, then the end of study visit will be allocated, based on study day, to the closest future scheduled study visit.

For scheduled visits, the analysis visits will be the actual (reported) visits.

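### Baseline FAF can predate dosing by up to 8 weeks (12 with agreement) with no repeat, so study-eye GA change at nominal Week 48 can include untreated growth and overstate 48-week growth by up to 16.7% (25.0%).

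*Protocol*

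**What the plan says.** - **Timing of dosing.** Protocol 7.1 schedules surgery within 8 weeks of screening and adds: "The 8-week screening period may be extended up to a maximum of 12 weeks, if agreed by the Sponsor Medical Monitor".
- **What is repeated.** If screening runs to 8–12 weeks, "standard ophthalmic exam, haematology/biochemistry, and visual acuity (BCVA/LLVA) assessments should be repeated". FAF joins the list only for 12–16 weeks after an intra-operative deferral, when "standard ophthalmic exam, haematology/biochemistry, visual acuity (BCVA/LLVA), and FAFs will be repeated". Protocol 8.2.3 does not count FAF as part of the standard ophthalmic examination.
- **FAF schedule.** Table 2 and Sections 7.1 and 7.6 place FAF at screening and next at Week 5. The readable pre-surgery assessments do not include it. Some lines there are redacted, but FAF is left readable elsewhere, so they are unlikely to hide one.
- **A second statement of the interval.** Protocol 4.4.1 allows re-screening "to allow the 8-week time interval between baseline assessment of the screening visit and dosing to be maintained". That does not sit easily with the 12-week extension.
- **Baseline and time axis.** SAP 3.1.1 fixes the starting value as follows: "Baseline values are defined as values from the last assessment prior to surgery for the study treatment administration". For FAF that is the screening image. The same section then draws the line at dosing: "All data collected after the treatment administration are defined as post-baseline". On the time axis it says: "For scheduled visits, the analysis visits will be the actual (reported) visits".
- **Analysis.** SAP 3.7 analyses study-eye change in GA area, and in its square root, with two MMRMs. The fixed effects are treatment (dose and route), visit, baseline size and their interactions with visit. Neither has a term for time since the baseline image.
- **Comparators.** Protocol 11.3.2: "The GA area size data will be compared to historical data on natural disease progression", including subjects' own pre-treatment data if available. The synopsis names the untreated fellow eye as the comparator.

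**The concern.** The lesion keeps growing between the screening image and surgery. That growth is untreated, yet it enters the change from baseline reported at each visit counted from dosing. A figure labelled as 48 weeks of post-treatment growth can cover up to 56 weeks, or 60 with an agreed extension.

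The protocol accepts that other baselines go stale after 8 weeks, since it repeats acuity and laboratory tests. It leaves out the image on which the anatomical endpoint rests.

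The historical comparison is most exposed. If the trial's Week 48 change is set against natural progression over 48 weeks, the denominators do not match and GT005 looks worse than it is. Protocol 11.3 says that interim analyses may inform internal development decisions, so a diluted signal could matter even without formal testing.

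**Working it through.** The documents give no GA growth rate, standard deviation, power figure or distribution of actual lags, so there is no stated figure to reproduce. Interval arithmetic is enough.

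**Inputs from the documents.** Lag L from baseline FAF to dosing: up to 8 weeks ordinarily, up to 12 with agreement (Protocol 7.1). Nominal visits: Week 48, and Week 96, the CSR horizon in SAP 3.1.

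**Assumptions.** Growth at a constant rate before dosing; a proportional slowing r after dosing.

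**1. Interval covered at Week 48.** 48 + 8 = 56 weeks; 48 + 12 = 60 weeks (59 to 61 with the ±7-day visit window).

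**2. Overstatement of growth since dosing.** Excess = L / (V × (1 − r)) at visit V; the growth rate cancels. With r = 0:

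| Lag | Week 48 | Week 96 |
|---|---|---|
| 4 weeks | 4/48 = 8.3% | 4/96 = 4.2% |
| 8 weeks | 8/48 = 16.7% | 8/96 = 8.3% |
| 12 weeks | 12/48 = 25.0% | 12/96 = 12.5% |

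If treatment slows growth, the excess relative to true post-dosing growth is larger. For a 12-week lag at Week 48 and r = 30%, it is 12 / (48 × 0.7) = 35.7%.

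**3. Sensitivity to the growth law.** If growth is linear on the square-root scale, at an assumed 0.2 to 0.4 mm/year from baseline areas of 1.25 to 17.5 mm², the 12-week excess in area at Week 48 is 20.9% to 24.3%. On the square-root scale it stays 25.0%.

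**4. Absolute size.** For assumed growth of 1 to 3 mm²/year, the excess is 0.15 to 0.46 mm² for an 8-week lag and 0.23 to 0.69 mm² for a 12-week lag.

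**5. Historical comparison over a nominal 48 weeks.** Apparent slowing = 1 − (L + 48 × (1 − r)) / 48. With r = 30%:
- L = 8: 1 − (8 + 33.6)/48 = 13.3%
- L = 12: 1 − (12 + 33.6)/48 = 5.0%

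**6. Historical comparison over the actual interval.** Apparent slowing = r × 48 / (48 + L). With r = 30%:
- L = 8: 0.30 × 48/56 = 25.7%
- L = 12: 0.30 × 48/60 = 24.0%

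The denominator error goes. What remains is the averaging of untreated with treated weeks.

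**7. Fellow-eye comparison.** Both eyes share the lag. If both grow at the same rate g before dosing, g × L cancels in the study-minus-fellow difference, which is unbiased. The percentage reduction is still diluted by 48 / (48 + L), so 30% appears as 24% when L = 12.

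**8. Dose and route contrasts.** A lag common to all groups cancels under the same growth assumption. A difference of d weeks in mean lag adds a spurious d/48 of 48-week growth. The documents give no value for d; a hypothetical 4 weeks would give 8.3%.

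**The case against.** The case for leaving the plan alone has real weight.

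- **The primary endpoint is untouched.** A reader might infer that the trial's main Week 48 result is inflated. It is not: that endpoint is the incidence of treatment-emergent adverse events. GA area is one of several secondary measures, and SAP 3.1 plans no hypothesis tests. This stands.
- **The direction runs against GT005.** Growth is overstated, so benefit is understated, not exaggerated. This stands, although a bias that hides a signal still misleads.
- **25.0% is a ceiling.** It needs a subject granted the full extension. The ordinary limit gives 16.7%, and actual lags may be shorter. This stands.
- **Distorted dose and route comparisons are not shown.** A reader might infer them from the staggered design: 14-day sentinel spacing in Part 1, screening allowed before the DSMB decision, and transfer from local to surgical sites. These make unequal lags plausible. The documents do not show that lags differ, and the same window applies to every cohort.
- **The fellow eye protects the difference.** It is the named comparator and is imaged by FAF too. The protection is partial: inclusion criterion 2 requires AMD but not GA in the fellow eye, and both GA models in SAP 3.7 are for the study eye only.
- **The historical bias is conditional.** The readable SAP gives no method for that comparison. The bias arises if a nominal interval is used and the historical data carry no similar lag. That is a reason to specify the method.

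**Conclusion.** The concern holds for absolute study-eye GA growth and for a historical comparison made over nominal time. Under constant growth with no slowing after dosing, a lag at the permitted limit overstates Week 48 growth by 16.7% ordinarily and 25.0% with an agreed extension; at Week 96 the figures are 8.3% and 12.5%. These are upper limits on the lag effect under that assumption, not estimates of typical bias, because the actual lags are not given.

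It does not follow that the primary endpoint is affected, that efficacy is overstated, or that dose and route contrasts are biased; the last needs lags that differ between groups. The matter is worth correcting because the historical comparison is planned, its interval is undefined in the readable SAP, and the fellow-eye contrast that would cancel the lag is not built into the GA models.

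**What to change.** Change the SAP; no new assessments are needed.

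1. **Historical comparison.** In SAP 3.7, state that growth rates for the comparison in Protocol 11.3.2 are computed over the actual time from the baseline FAF image to the follow-up image. Note that such a rate still averages the untreated lag with treated time: with a 12-week lag, a true 30% slowing appears as 24%.
2. **Report the lag.** Summarise days from baseline FAF to dosing by dose and route. SAP 3.1.1 already defines negative study days before treatment, so the lag is the study day of the baseline image. This table shows whether group contrasts are at risk.
3. **Sensitivity MMRM.** Refit both GA models with the lag as a covariate. If growth is linear on the modelled scale, the lag adds the same amount at every visit, so one main effect suffices. Keep this as a sensitivity analysis: least-squares means at zero lag sit at or beyond the edge of the data, and escalation cohorts may have only 3 to 5 subjects.

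Separately, the 8-week interval in Protocol 4.4.1 and the 12-week extension in 7.1 should be reconciled.

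The cost is a few lines of SAP text, one table, one degree of freedom in each sensitivity model, and the assumption in those models of a common pre-dosing growth rate.
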